3. INTRODUCTION

This SAP has been developed after review of the Clinical Study Protocol (final version dated 21 October 2016).

This SAP describes the planned analysis of the safety, tolerability and pharmacokinetic (PK) data from this study. A detailed description of the planned TFLs to be presented in the clinical study report (CSR) is provided in the accompanying TFL shell document.

The intent of this document is to provide guidance for the statistical and PK analyses of data. In general, the analyses are based on information from the protocol, unless they have been modified by agreement between Eli Lilly and Company and Covance Early Clinical (EC) Biometrics. A limited amount of information concerning this study (e.g., objectives, study design) is given to help the reader's interpretation. This SAP must be signed off prior to first subject administration for this study. When the SAP and TFL shells are agreed upon and finalized, they will serve as the template for this study's CSR.

This SAP supersedes the statistical considerations identified in the protocol; where considerations are substantially different, they will be so identified. If additional analyses are required to supplement the planned analyses described in this SAP, they may be performed and will be identified in the CSR. Any substantial deviations from this SAP will be agreed upon between Eli Lilly and Company and Covance EC Biometrics and identified in the CSR. Any minor deviations from the TFLs may not be documented in the CSR.

This SAP is written with consideration of the recommendations outlined in the International Council on Harmonisation (ICH) E9 Guideline entitled Guidance for Industry: Statistical Principles for Clinical Trials¹ and the ICH E3 Guideline entitled Guidance for Industry: Structure and Content of Clinical Study Reports².

4. STUDY OBJECTIVES

4.1 Primary Objective

The primary objective is to evaluate the effect of LY3314814 on the PK of rosuvastatin in healthy subjects.

4.2 Secondary Objectives

The secondary objectives are:

- To assess the safety of LY3314814 when coadministered with rosuvastatin in healthy subjects.
- To determine the effect of rosuvastatin on the PK of LY3314814.

4.3 Exploratory Objective

CCI

5. STUDY DESIGN

This is a Phase 1, open-label, fixed-sequence, 2-period crossover study to evaluate the PK of rosuvastatin administered alone and after 7 days of treatment with LY3314814 in Caucasian healthy male subjects and female subjects not of childbearing potential. Figure 1 illustrates the study design. All subjects will receive each of the following treatments:

Period 1: single oral dose of 20 mg rosuvastatin on Day 1.

Period 2: oral doses of 50 mg LY3314814 once daily (QD) on Days 1 to 12 with a single 20 mg rosuvastatin oral dose coadministered on Day 8.

Period 2 will immediately follow Period 1, with no anticipated break between periods. Subjects will reside at the clinical research unit (CRU) for the duration of both study periods.

[figure not shown]

Figure 1. Illustration of study design for Protocol I8D-MC-AZEB

Each subject will provide informed consent for study participation and will undergo a screening examination within 45 days prior to enrollment. Subjects who meet all other screening eligibility criteria will return for a second screening visit, at least 21 days prior to enrollment, when samples will be collected for genotype analysis.

In Period 1, subjects will be admitted to the CRU on Day -1. On the morning of Day 1, after an overnight fast of at least 8 hours, a single oral dose of 20 mg rosuvastatin will be administered and will be followed by a fast of at least 4 hours. Blood samples will be collected predose and up to 120 hours postdose (Day 6) for measurement of plasma rosuvastatin concentrations.

There will be a washout period of at least 7 days between the single dose of rosuvastatin on Day 1 in Period 1 and the first dose of LY3314814 on Day 1 in Period 2.

In Period 2, oral doses of 50 mg LY3314814 QD will be taken in the morning of Days 1 to 12. On the morning of Day 7, LY3314814 will be administered after an overnight fast of at least

8 hours and followed by a fast of at least 4 hours. On Day 8, after an overnight fast of at least 8 hours, a single oral dose of 20 mg rosuvastatin will be coadministered with 50 mg LY3314814 and will be followed by a fast of at least 4 hours. On Days 7 and 8, blood samples will be collected predose and up to 24 hours after the LY3314814 dose to determine plasma LY3314814 concentrations. Blood samples will be collected predose on Day 8 and up to 120 hours postdose (Day 13) for measurement of plasma rosuvastatin concentrations. Subjects will be discharged on Day 13 of Period 2 after all assessments have been completed. A follow-up visit will occur at least 7 days following the final LY3314814 dose in Period 2.

Safety and tolerability will be assessed throughout the study by means of vital sign measurements, clinical laboratory tests, electrocardiograms (ECGs), Columbia-Suicide Severity Rating Scale (C-SSRS), physical examinations (as indicated), and adverse event (AE) recording.

6. TREATMENTS

The following is a list of the study treatment names that will be used in the safety TFLs.

Study Treatment Name	Treatment order in TFL
20 mg rosuvastatin (D1)	1
50 mg LY3314814 QD (D1 – D7)	2
50 mg LY3314814 QD + 20 mg rosuvastatin (\geq D8)	3

D = Day

The following is a list of the study treatment names that will be used in the PK TFLs.

Study Treatment Name	Treatment order in TFL
20 mg rosuvastatin	1
50 mg LY3314814 QD + 20 mg rosuvastatin	2
50 mg LY3314814 QD	3

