9.4 Safety and Tolerability Assessments

9.4.1 Adverse events

Where changes in severity are recorded in the Case Report Form (CRF), each separate severity of the AE will be reported in the listings, only the most severe will be used in the summary tables. A pre-existing condition is defined as an AE that starts before the subject has provided written informed consent and is ongoing at consent. A non-treatment emergent AE is defined as an AE which starts after informed consent but prior to the first dose. A treatment-emergent AE is defined as an AE which occurs postdose or which is present prior to dosing and becomes more severe postdose. AEs by day of onset will be presented.

All AEs will be listed. Treatment-emergent AEs will be summarized by treatment, severity and relationship to the study drug. The frequency (the number of AEs, the number of subjects experiencing an AE and the percentage of subjects experiencing an AE) of treatment-emergent AEs will be summarized by treatment, Medical Dictionary for Regulatory Activities (MedDRA) version 19.1 system organ class and preferred term. The summary and frequency AE tables will be presented for all causalities and those considered related to the study drug. Any serious AEs will be tabulated.

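### The combination safety column has no end date, so crude adverse-event percentages set at least 11 days beside about 7

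*SAP*

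**What the plan says.** SAP Section 6 names three columns for the safety tables: "20 mg rosuvastatin (D1", "50 mg LY3314814 QD (D1 – D7" and "50 mg LY3314814 QD + 20 mg rosuvastatin (\geq D8". Only the LY3314814-alone label gives both a start and an end.

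SAP Section 9.4.1 states that "Treatment-emergent AEs will be summarized by treatment, severity and relationship to the study drug", and adds frequency tables by treatment with the count of events and the count and percentage of subjects affected. It treats any event after dosing, or any worsening after dosing, as treatment-emergent. It sets no cut-off after the last dose and makes no adjustment for exposure. It also plans a display of events by day of onset.

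The timing comes from SAP Section 5. LY3314814 is given as "oral doses of 50 mg LY3314814 once daily (QD) on Days 1 to 12", subjects leave the unit on Period 2 Day 13, and "A follow-up visit will occur at least 7 days following the final LY3314814 dose in Period 2". For rosuvastatin alone, "There will be a washout period of at least 7 days between the single dose of rosuvastatin on Day 1 in Period 1", counted up to when LY3314814 starts. The section also says that "Period 2 will immediately follow Period 1, with no anticipated break between periods". The protocol's Schedule of Activities includes adverse-event assessment at follow-up.

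**The concern.** The incidence of treatment-emergent events is a secondary endpoint for the objective of assessing LY3314814 given with rosuvastatin (Protocol Table AZEB.1), and Protocol Section 10.3.1.1 asks for incidence for each treatment. With no safety inference planned (SAP Section 9.4.8), readers will compare the three percentages by eye.

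Those percentages cover different lengths of time. They also cover different mixtures of dosing days, days just after dosing, and outpatient days. A difference between columns could reflect the interaction, the length of the window or the number of doses in it, and the table would not show which. The protocol's own definition (Appendix 1) ties a treatment-emergent event to a defined treatment period. The SAP leaves two of its three periods without an end, while SAP Section 11 reports no change from the protocol analyses.

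**Working it through.** The plan states no time at risk for any safety column, so there is no figure of its own to reproduce here. The windows follow from the schedule.

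**Windows (elapsed days)**
- Combination: last LY3314814 dose on Day 12, follow-up at least 7 days later, so 12 + 7 = Day 19 or later. From Day 8 that is 19 − 8 = 11 days at least (12 if both end dates are counted).
- LY3314814 alone: Days 1 to 7, 7 days.
- Rosuvastatin alone: Period 1 Day 1 to the first LY3314814 dose, at least 7 days and about 7 if the periods run on as planned. The label itself gives no end.
- Ratio of combination to LY3314814 alone: 11/7 = 1.57 at least.

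**LY3314814 doses in each window**
- LY3314814 alone: 7 doses in 7 days, 1 per day.
- Combination: Days 8 to 12, 5 doses in at least 11 days, 5/11 = 0.45 per day at most.
- Combination up to discharge on Day 13: 5 doses in 13 − 8 = 5 days, 1 per day.
- Combination after discharge: at least 19 − 13 = 6 days, no doses.

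**Case A: constant daily rate, no interaction.** The documents give no event rate, so the 7-day incidence p is an assumption. Incidence over 11 days = 1 − (1 − p)^(11/7).

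| Assumed 7-day incidence | Over 11 days | Ratio | Subjects of 24 |
|---|---|---|---|
| 10% | 15.3% | 1.53 | 2.4 v 3.7 |
| 20% | 29.6% | 1.48 | 4.8 v 7.1 |
| 30% | 42.9% | 1.43 | 7.2 v 10.3 |
| 40% | 55.2% | 1.38 | 9.6 v 13.2 |

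Even here chance matters. With 24 subjects and the two columns treated as independent, the combination count exceeds the LY3314814-alone count with probability 0.63, 0.73 and 0.79 at 10%, 20% and 30%.

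**Case B: events only on LY3314814 dosing days.** Incidence = 1 − (1 − p)^(5/7). An assumed 20% becomes 14.7%, so the combination column looks better.

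**Case C: exposure continues after the last dose.** The half-life is about 18 hours (Protocol Section 3.2.1.1), so five half-lives = 5 × 18/24 = 3.75 days. Exposed time from Day 8 is then 4 + 3.75 = 7.75 days, and 20% becomes 1 − 0.8^(7.75/7) = 21.9%, close to parity.

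**Case D: event rate fades from Period 2 Day 1 with half-life h.** With k = ln 2/h, the ratio of cumulative hazard is (e^(−7k) − e^(−18k))/(1 − e^(−7k)). It is 0.66 at h = 7 days, 1.15 at h = 20 days, and 1 at about h = 13.6 days. With faster fading than that, the combination column is expected to hold fewer events than LY3314814 alone.

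**The case against.** The strongest reply is that the extra time carries little drug. The days beyond dosing are spent mostly outside the unit, and the column holds fewer LY3314814 doses than its comparator. A reader might infer that the longer window must make coadministration look less safe. The documents do not support that: Cases B and D reverse the direction and Case C leaves almost no gap. This part of the reply stands in full. It does not make the columns comparable, because a distortion of unknown direction still cannot be separated from a drug effect.

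Three further points limit the concern:
- Section 6 is a list of column names. No sentence assigns follow-up events to the combination, and the table shells that might do so are a separate document not available here. The assignment is inferred from the open label, although no other column could receive those events.
- Seven days for rosuvastatin alone is a minimum drawn from the washout, not a stated window.
- The protocol endpoint is incidence, without a formal comparison between treatments, and safety is descriptive throughout.

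The plan also has safeguards: full listings, separate tables of drug-related events, and the onset-day display. The last lets a careful reader separate early from late events, but it leaves the by-treatment percentages as they are.

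**Conclusion.** The point holds as a lack of comparability. As labelled, the combination column covers at least 1.57 times the days of LY3314814 alone, at less than half the dosing density, and the incidence tables adjust for neither. The day counts rest on the SAP schedule and on reading the open label literally. A later follow-up visit lengthens the window further, and the plan sets no upper limit on that visit.

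The percentages in the working rest on assumed event rates and on the assumed shape of the hazard. Across those shapes, an assumed 20% for LY3314814 alone corresponds to anything from 14.7% to 29.6% in the combination column with no interaction at all. A claim of bias in one known direction would therefore be too strong. The consequence is modest, since the safety analysis is descriptive and the onset-day display gives partial protection. The correction is cheap enough to be worth making.

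**What to change.** In SAP Sections 6 and 9.4.1:
- Keep the total for Day 8 onward, and split it by onset into an in-unit part (Day 8 to discharge on Day 13) and a follow-up part after discharge. No event is dropped. The in-unit part has the same dosing density as LY3314814 alone, one dose per day.
- State that the rosuvastatin-alone window ends at the first LY3314814 dose.
- Print subject-days at risk and treatment-emergent events per 100 subject-days under every column, including both parts and the total.

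The split and the rates are needed together: a rate on the undivided total would average 5 dosing days with at least 6 days after discharge.

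A hard cut at Day 14 is not recommended. Five half-lives after the Day 12 dose run to about Day 15.75, so the cut would move possibly drug-related events out of the combination total. It would also set 7 dosing days against 5 dosing days plus 2 without a dose.

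The cost is SAP wording and a slightly larger table. All the data are already collected.

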7. SAMPLE SIZE JUSTIFICATION

Up to 28 subjects may be enrolled in order that 24 subjects complete the study.

For rosuvastatin area under the concentration curve (AUC), the intrasubject variability (coefficient of variation [CV%]) was estimated to be 25.5% by assuming intrasubject variability comprised half of the total variability of 51% (CDER 2003); Martin et al. (2016) estimated the intrasubject variability of rosuvastatin AUC to be 21%. A sample size of 24 subjects will

provide 92.3% probability that the estimated AUC geometric mean ratio will be within 0.15 of the upper and lower bounds of the 90% confidence interval (CI) in the log scale, which corresponds to approximately 0.162 in the natural scale.

While this study is not powered for the maximum observed drug concentration (C_{max}) geometric mean ratio to be within 0.15 of the upper and lower bounds of the 90% CI in the log scale, the C_{max} power calculations are described here to give the expected results context. For rosuvastatin C_{max} , the intrasubject variability was estimated to be 35.9% by assuming intrasubject variability comprised half of the total variability of 71.8% (CDER 2003); Martin et al. (2016) estimated the C_{max} intrasubject variability of rosuvastatin to be 34%. A sample size of 24 subjects will provide 19.6% probability that the estimated C_{max} geometric mean ratio will be within 0.15 of the upper and lower bounds of the 90% CI in the log scale.

8. DEFINITION OF ANALYSIS POPULATIONS

The “Safety” population will consist of all enrolled subjects, whether or not they completed all protocol requirements.

The PK analyses will be conducted on the “Full analysis set”. This set includes all data from all subjects who received at least one dose of study drug and have evaluable PK data. Subjects may be excluded from the PK summary statistics and statistical analysis if a subject has an AE of vomiting that occurs at or before 2 times median time to maximum concentration (t_{max}).

Additional exploratory analyses of the data will be conducted as deemed appropriate. Study results may be pooled with the results of other studies for population PK analysis purposes to avoid issues with post-hoc analyses and incomplete disclosures of analyses.

All protocol deviations that occur during the study will be considered for their severity/impact and will be taken into consideration when subjects are assigned to analysis populations.

9. STATISTICAL METHODOLOGY

9.1 General

Data listings will be provided for all data that is databased. Summary statistics and statistical analysis will only be presented for data where detailed in this SAP. For continuous data, summary statistics will include the arithmetic mean, arithmetic standard deviation (SD), median, min, max and N; for log-normal data (e.g. the PK parameters: AUCs and C_{max}) the geometric mean and geometric CV% will also be presented. For categorical data, frequency count and percentages will be presented. Data listings will be provided for all subjects up to the point of withdrawal, with any subjects excluded from the relevant population highlighted. Summary statistics and statistical analyses will generally only be performed for subjects included in the relevant analysis population. For the calculation of summary statistics and statistical analysis, unrounded data will be used.

Mean change from baseline is the mean of all individual subjects' change from baseline values. Each individual change from baseline will be calculated by subtracting the individual subject's

baseline value from the value at the timepoint. The individual subject's change from baseline values will be used to calculate the mean change from baseline using a SAS procedure such as Proc Univariate.

Data analysis will be performed using SAS® Version 9.3 or greater.

9.2 Demographics and Subject Disposition

Subject disposition will be listed. The demographic variables age, sex, race, ethnicity, country of enrolment, site ID, body weight, height and body mass index will be summarized and listed. Furthermore, genotyping data will be summarised and listed.

9.3 Pharmacokinetic Assessment

9.3.1 Pharmacokinetic Analysis

PK parameter estimates will be determined using non-compartmental procedures in validated software program (Phoenix WinNonlin Version 6.4.1 or later).

Plasma concentrations of rosuvastatin will be used to determine the following PK parameters, when possible:

Parameter	Units	Definition
AUC(0-t _{last})	ng.h/mL	area under the concentration versus time curve from time zero to time t, where t is the last time point with a measurable concentration
AUC(0-∞)	ng.h/mL	area under the concentration versus time curve from zero to infinity
%AUC(t _{last} -∞)	%	percentage of AUC(0-∞) extrapolated
C _{max}	ng/mL	maximum observed drug concentration
t _{max}	h	time of maximum observed drug concentration
t _{1/2}	h	half-life associated with the terminal rate constant (λ _z) in non-compartmental analysis
CL/F	L/h	apparent total body clearance of drug calculated after extra-vascular administration
V _z /F	L	apparent volume of distribution during the terminal phase after extra-vascular administration
V _{ss} /F	L	apparent volume of distribution at steady state after extra-vascular administration

An alternative AUC measure, such as AUC to a common time point, may be calculated if AUC(0-∞) cannot be reliably calculated.

Plasma concentrations of LY3314814 will be used to determine the following PK parameters, when possible:

Parameter	Units	Definition
$AUC_{\tau, ss}$	ng.h/mL	area under the concentration versus time curve during one dosing interval at steady state
$C_{max, ss}$	ng/mL	maximum observed drug concentration at steady state
$t_{max, ss}$	h	time of maximum observed drug concentration at steady state
CL_{ss}/F	L/h	apparent total body clearance of drug calculated after extra-vascular administration at steady state

Additional PK parameters may be calculated, as appropriate. The software and version used for the final analyses will be specified in the CSR. Any exceptions or special handling of data will be clearly documented within the final study report.

Formatting of tables, figures and abbreviations will follow the Eli Lilly Global PK/PD/TS Tool: NON-COMPARTMENTAL PHARMACOKINETIC STYLE GUIDE. The version of the tool effective at the time of PK analysis will be followed.

General PK Parameter Rules

- Actual sampling times will be used in the final analyses of individual PK parameters, except for non-bolus pre-dose sampling times which will be set to zero. For non-bolus, multiple dose profiles, the pre-dose time will be set to zero unless a time deviation falls outside of the protocol blood collection time window which is considered to impact PK parameter derivation.
- C_{max} and t_{max} will be reported from observed values. If C_{max} occurs at more than one time point, t_{max} will be assigned to the first occurrence of C_{max} .
- AUC parameters will be calculated using a combination of the linear and logarithmic trapezoidal methods (linear-log trapezoidal rule). The linear trapezoidal method will be applied up to t_{max} and then the logarithmic trapezoidal method will be used after t_{max} . The minimum requirement for the calculation of AUC will be the inclusion of at least three consecutive plasma concentrations above the lower limit of quantification (LLOQ), with at least one of these concentrations following C_{max} . AUC(0-∞) values where the percentage of the total area extrapolated is more than 20% will be flagged. Any AUC(0-∞) value excluded from summary statistics will be noted in the footnote of the summary table.
- Half-life ($t_{1/2}$) will be calculated, when appropriate, based on the apparent terminal log-linear portion of the concentration-time curve. The start of the terminal elimination phase for each subject will be defined by visual inspection and generally will be the first point at which there is no systematic deviation from the log-linear decline in plasma concentrations. Half-life will only be calculated when a reliable estimate for this parameter can be obtained comprising of at least 3 data points. If $t_{1/2}$ is estimated over a time window of less than 2 half-lives, the values will be flagged in the data listings. Any $t_{1/2}$ value excluded from summary statistics will be documented in the footnote of the summary table.

- A uniform weighting scheme will be used in the regression analysis of the terminal log - linear portion of the concentration-time curve.
- The parameters based on predicted C_{last} will be reported.

Individual PK Parameter Rules

- Only quantifiable concentrations will be used to calculate PK parameters with the exception of special handling of certain concentrations reported below the lower limit of quantitation (BQL). Plasma concentrations reported as BQL will be set to a value of zero when all of the following conditions are met:
 - The compound is non-endogenous.
 - The samples are from the initial dose period for a subject or from a subsequent dose period following a suitable wash-out period.
 - The time points occur before the first quantifiable concentration.
- All other BQL concentrations that do not meet the above criteria will be set to missing.
- Also, where two or more consecutive concentrations are BQL towards the end of a profile, the profile will be deemed to have terminated and therefore any further quantifiable concentrations will be set to missing for the calculation of the PK parameters unless it is considered to be a true characteristic of the profile of the drug.

Individual Concentration vs. Time Profiles

- Individual concentrations will be plotted utilizing actual sampling times.
- The terminal point selections will be indicated on a semi-logarithmic plot.

Average Concentration vs. Time Profiles

- The average concentration profiles will be graphed using scheduled (nominal) sampling times.
- The average concentration profiles will be graphed using arithmetic average concentrations.
- The pre-dose average concentration for single-dose data from non-endogenous compounds will be set to zero. Otherwise, only quantifiable concentrations will be used to calculate average concentrations.
- Concentrations at a sampling time exceeding the sampling time window specified in the protocol, or $\pm 10\%$, will be excluded from the average concentration profiles.

- Concentrations excluded from the mean calculation will be documented in the final study report.
- A concentration average will be plotted for a given sampling time only if 2/3 of the individual data at the time point have quantifiable measurements that are within the sampling time window specified in the protocol or $\pm 10\%$. An average concentration estimated with less than 2/3 but more than 3 data points may be displayed on the mean concentration plot if determined to be appropriate and will be documented within the final study report.

Treatment of Outliers during Pharmacokinetic Analysis

Application of this procedure to all PK analyses is not a requirement. Rather, this procedure provides justification for exclusion of data when scientifically appropriate. This procedure describes the methodology for identifying an individual value as an outlier for potential exclusion, but does not require that the value be excluded from analysis. The following methodology will not be used to exclude complete profiles from analysis.

Data within an Individual Profile

A value within an individual profile may be excluded from analysis if any of the following criteria are met:

- For PK profiles during multiple dosing, the concentration of the pre-dose sample exceeds all measured concentrations for that individual in the subsequent post-dose samples.
- For PK profiles during single dosing of non-endogenous compounds, the concentration in a pre-dose sample is quantifiable.
- For any questionable datum that does not satisfy the above criteria, the profile will be evaluated and results reported with and without the suspected datum.

Data between Individual Profiles

1. If $n < 6$, then the dataset is too small to conduct a reliable range test. Data will be analyzed with and without the atypical value, and both sets of results will be reported.
2. If $n \geq 6$, then an objective outlier test will be used to compare the atypical value to other values included in that calculation:
 - a. Transform all values in the calculation to the logarithmic domain.
 - b. Find the most extreme value from the arithmetic mean of the log transformed values and exclude that value from the dataset.
 - c. Calculate the lower and upper bounds of the range defined by the arithmetic mean $\pm 3 \times SD$ of the remaining log-transformed values.

- d. If the extreme value is within the range of arithmetic mean $\pm 3 \times \text{SD}$, then it is not an outlier and will be retained in the dataset.
- e. If the extreme value is outside the range of arithmetic mean $\pm 3 \times \text{SD}$, then it is an outlier and will be excluded from analysis.

If the remaining dataset contains another atypical datum suspected to be an outlier and $n \geq 6$ following the exclusion, then repeat step 2 above. This evaluation may be repeated as many times as necessary, excluding only one suspected outlier in each iteration, until all data remaining in the dataset fall within the range of arithmetic mean $\pm 3 \times \text{SD}$ of the log-transformed values.

Reporting of Excluded Values

Individual values excluded as outliers will be documented in the final report. Approval of the final report will connote approval of the exclusion.

